## **5.3 Recruitment Methods**

### **5.3.1 Number of Subject**

#### **Needed Veterans**

276 total participants (138 per study arm) will be needed to ensure > 80% power for this two-arm trial, accounting for the clustering effect of CBTw group cohort and potential attrition of 13%. The study sample will include around 50% minority participants, and 5% Hispanic; these figures are consistent with CBTw pilot studies which included 48% African American participants. These are also representative of the mean number of non-white Veterans served at RLR, Hines, and St. Louis. In FY18, 48.7% of Veterans at these facilities were non-white, 46.2% Caucasian, and 2.7% identified as Hispanic or Latino. In the CBTw pilot studies, 10% women Veterans were recruited, consistent with gender distribution of Veterans served by the 3 study facilities (mean of 10.8% of Veterans identify as female in FY18). In WORKWELL, comparable numbers of women Veterans will be recruited. Data analyses will examine differences in outcomes based on gender and ethnicity, although these analyses may be underpowered to

detect significant differences.

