## **5.5 Inclusion/Exclusion Criteria**

### **5.5.1 Veterans**

#### ***Inclusion criteria***

1) Unemployment, defined as no current participation in a competitive job; 2) a competitive work goal; 3) Presence of a serious mental illness (required to receive SE services); 4) Receiving SE services; 5) Age 18 or older.

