#### *Competitive Work Outcomes (Hypothesis 1)*

For the outcome, total weeks worked in competitive jobs, three-level linear regression models will be used to test the effects of CBTw + SE compared to psychoeducation + SE over time, with predictors of study arm, arm by time interaction, site, and interaction between site and key predictors, covariates, as well as random effects to accommodate the potential non-independence due to repeated measures and group cohort effects. The time effects could be linear or nonlinear; these possibilities will be examined by treating time as continuous or categorical. If the outcomes are not normally distributed, robust maximum likelihood estimation method will be used to correct the standard error estimates for nonnormality. In the case of excess of zeros for this outcome, hurdle negative binomial models, a reliable method to analyze zero inflated longitudinal data of this nature, will be utilized. For the binary outcome, steady competitive work status across the 12-month study period, two-level logistic regression model will be used with the same set of predictors as in the linear models, with random effects to accommodate the potential non-independence due to group cohort effects.

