Statistical Analysis Plan

Protocol Number: CIRB 20-08

Work as a determinant of health: A pragmatic trial of enhanced cognitive behavioral therapy to competitive work and wellness in veterans with serious mental illness (WORKWELL)

Funding Agency: HSR&D

9/30/2025

Analysis Plan

Statistical Considerations

Sample size and power

276 total participants will be needed to ensure > 80% power for this two-arm trial, accounting for the clustering effect of CBTw group cohort and potential attrition of 13%.

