Aim 1: Work outcomes. The primary analysis is intention-to-treat and the primary outcome is total weeks worked in competitive jobs with primary endpoints of 6 and 9 months. Power estimate for total weeks worked was calculated using simulated data from a three-level linear regression model to account for the nested structure of the data. Simulation studies are the most flexible method for power analysis which can be tailored to any kinds of analyses. SAS 9.4 was used to generate 1000 datasets from each hypothesized model with plausible effect sizes for parameters of interest based on pilot data. Power estimates are based on the percentage of the datasets (replications) in which the parameters were significant. Based on the open trial pilot data, an ICC of .077 was estimated for the clustering effect of cohort and an ICC of .2 for repeated measures. Our pilot data show that CBTw significantly increased total weeks worked at 6 months ($f^2 = .15$). It is anticipated that there will be a larger increase in total weeks worked over time for the treatment arm. With the target sample size, there will be 97.6% power to detect even a small study arm by time interaction effect ($f^2 = .03$) with type I error set at .05. Further, the outcome distribution is likely to be non-normal. Although power will be attenuated by this non-normality, power to detect the target effects is still expected to be sufficient (>80%). For the binary outcome of achievement of steady competitive work, CBTw pilot data show that 49% of participants who were unemployed at baseline became steady workers at 6 months. In WORKWELL, it is expected that 5-10% more participants will acquire work and become steady workers during by the 9 month follow-up. Thus, power estimates may be conservative. In the control arm, it is anticipated that approximately 34% will become competitively employed and a lesser number will be steady workers by 9 months, based on VHA program evaluation data reporting 1-year SE outcomes. Based on the effect size, simulated data was used from two level logistic regression models, finding that the target sample size will provide > 99% power to detect the treatment effect, accounting for a conservative estimate of 13% attrition. If more participants gain competitive employed in the control arm (~50%), there will be >80% power to detect this effect.

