Hypothesis 1: For the outcome, total weeks worked in competitive jobs, three-level linear regression models will be used to test the effects of CBTw + SE compared to psychoeducation + SE over time, with predictors of study arm, arm by time interaction, site, and interaction between site and key predictors, covariates, as well as random effects to accommodate the potential non-independence due to repeated measures and group cohort effects. The time effects could be linear or nonlinear; these possibilities will be examined by treating time as continuous or categorical. If the outcomes are not normally distributed, robust maximum likelihood estimation method will be used to correct the standard error estimates for nonnormality. In the case of excess of zeros for this outcome, hurdle negative binomial models, a reliable method to analyze zero inflated longitudinal data of this nature, will be utilized. For the binary outcome, steady competitive work status across the 9-month study period, two-level logistic regression model will be used with the same set of predictors as in the linear models, with random effects to accommodate the potential non-independence due to group cohort effects.

Aim 2 Analyses: Health and Recovery Outcomes

To test **Hypothesis 2a**, Two-level linear regression models accounting for the nested nature of the data (repeated measures nested within individuals) will be used to examine the effects of CBTw + SE services compared to psychoeducation + SE on the change of each of the continuous outcomes including recovery (RAS), health-related quality of life (PCS & MCS), symptoms (DSM), and suicidality (SSI) over time (baseline and 3-, 6-, 9-months follow-ups). The scores of the outcome measures are calculated by averaging the corresponding items. The models are the same as those in Aim 1 analysis except that the outcomes are different. It is hypothesized that CBTw + SE will lead to a greater improvement on the health and recovery outcomes (indicated by a significant arm by time effect). If the outcomes are not normally distributed, robust maximum likelihood estimation method will be used to correct the standard error estimates for nonnormality.

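### The Aim 1 model does not say how participant and cohort differences grow over time, so the 5% error rate of the arm-by-time test on weeks worked is not secured

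*SAP*

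**What the plan says.** - **Power (SAP, Sample size and power, Aim 1).** The simulation took "an ICC of .077 was estimated for the clustering effect of cohort and an ICC of .2 for repeated measures" and reports that "there will be 97.6% power to detect even a small study arm by time interaction effect", at f² = .03 and type I error .05. The SAP also says that the sample size allows for cohort clustering and 13% attrition.
- **Analysis (SAP, Aim 1 Analyses, Hypothesis 1).** Three-level linear models contain arm, arm by time, site and covariates, with "random effects to accommodate the potential non-independence due to repeated measures and group cohort effects". Time may be continuous or categorical. Neither document states random slopes, a residual covariance, or a cohort-by-time term.
- **Safeguards (protocol 5.6 Data Analysis, Hypothesis 1; same in the SAP).** If the outcome is non-normal, "robust maximum likelihood estimation method will be used to correct the standard error estimates for nonnormality". The level at which these errors are clustered is not given. Excess zeros lead to a hurdle negative binomial model.
- **Starting point (protocol 5.5.1, Inclusion criteria).** "Unemployment, defined as no current participation in a competitive job".
- **Outcome timing (protocol 5.6 Study Evaluations).** Total weeks are analyzed at every assessment point. Whether each value is a running total or a count since the last visit is not said.

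**The concern.** One ICC per level describes a process with the same variance at every visit and the same correlation between any two visits. A running total that starts at zero for everyone does not behave that way: its spread grows, and neighbouring visits correlate more strongly than distant ones. Participants and cohorts then differ mainly in slope.

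Arm by time is the term the SAP powers. If the fitted model has only intercepts at participant and cohort level, real differences in slope are not counted in its standard error, which is then too small. An ineffective CBTw could be declared effective on the primary outcome more often than 1 time in 20. On that reading the stated allowance for cohort clustering would not reach the tested term either.

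**Working it through.** **1. The plan's own figure.** Inputs are f² = .03, 276 participants (138 per arm) or about 240 after 13% attrition, cohort ICC .077, repeated-measures ICC .2 and cohorts of up to 8 (protocol 5.2.2). Two-sided testing is assumed. Noncentrality is λ = f² × observations ÷ design effect. The design effects are 1 + 7 × .077 = 1.539 (cohort) and 1 + 2 × .2 = 1.4 (three visits).

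| Variant | λ | Power |
|---|---|---|
| 240 × 3, repeated measures only | .03 × 720 / 1.4 = 15.4 | 97.5% |
| 276 × 3, cohort only | .03 × 828 / 1.539 = 16.1 | 98.0% |
| 240 × 3, both | .03 × 720 / (1.4 × 1.539) = 10.0 | about 88% |

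A direct calculation in a constant-correlation model with 240 participants and three visits gives 99.6% or more. The 97.6% falls among plausible variants. It can be neither uniquely reproduced nor refuted, because the scale of f², the number of occasions and the handling of attrition are not given.

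**2. Why intercepts do not help.** A participant's slope is Σ cⱼyⱼ with Σ cⱼ = 0. A participant or cohort intercept b contributes b × Σ cⱼ = 0. Variation in slope does not cancel, and slopes shared within a cohort do not average out over its members.

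**3. A hand check.** One simulated scenario (34% employed, mean job length 26 weeks, cohort ICC about .04 at week 26 and .05 at week 39) gave cumulative weeks at 13, 26 and 39 weeks with SDs of 2.2, 5.2 and 8.3. Correlations were .83 (13 with 26), .67 (13 with 39) and .91 (26 with 39).

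- Mean variance: (4.84 + 27.04 + 68.89) / 3 = 33.59.
- Mean covariance: (9.50 + 12.23 + 39.28) / 3 = 20.34.
- Implied ICC: 20.34 / 33.59 = .61, against the stated .2.
- Residual variance in a random-intercept model: 33.59 − 20.34 = 13.25. The model's variance for last minus first visit is 2 × 13.255 = 26.5.
- Actual variance of that difference: 4.84 + 68.89 − 2 × 12.23 = 49.3.
- Ratio: 49.3 / 26.5 = 1.86. Type I error: P(|Z| > 1.96 / √1.86) = P(|Z| > 1.44) = 15%.

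This counts only the variance understated within participants. Adding the correlation between cohort members, the simulation of the same scenario rejected 22.9%.

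**4. Simulated null rejection at nominal 5%.** Weekly job starts and losses were simulated for 120 completers per arm in cohorts of 8, usually with 2,000 to 3,000 trials per scenario. Three separately written simulations agree within the ranges shown. Cohort differences are near the stated ICC (roughly .04 to .11).

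| Model | No cohort effect | Cohorts differ in growth |
|---|---|---|
| Random intercepts, linear time, model-based SE, cumulative weeks, 3 or 4 occasions | 14-25% | 23-39% |
| Same, categorical time (joint test) | 7-12% | 13-21% |
| Participant slopes or participant-level robust SE | 4-6% | 9-15% |

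With five occasions, from a zero baseline to week 52, the first model gave 29-31% with no cohort effect. Counting weeks per interval with linear time and random intercepts gave about 9-19%. Clustering on cohort gave 4-6% with a cohort-level t test and about 6-9% with an uncorrected cohort-level sandwich estimator.

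A fitted mixed model on 150 null trials (three visits, no cohort effect) rejected 18.7% with random intercepts, the same as the closed form on those trials, and 6.0% with random slopes. A separate 150-trial three-level fit rejected 12% (Monte Carlo standard error 2.7 points).

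**The case against.** The two ICCs are inputs to the power simulation. The analysis section does not confine the model to random intercepts, and silence about slopes is not a decision to leave them out. The largest figures need several unstated choices together: intercepts only, linear time, model-based errors and running totals. The SAP itself expects non-normal data, so robust estimation would probably be used. In a three-level likelihood the independent units are cohorts, so a sandwich estimator would ordinarily be summed over cohorts, which gives close to nominal error. With many zeros the linear model may give way to the hurdle model, which no simulation here covers. The simulated repeated-measures ICC is about .6 against the pilot's .2, and the job-loss and re-hire rates are assumed.

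All of this stands, and it rules out two stronger readings. A reader might infer that the primary test will reject some 15-35% of null trials. The documents do not support that, because they do not fix the model that would produce it. A reader might also infer that the 97.6% power is false. It is not shown to be: plausible variants give nearly the same figure.

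The objection does not show that the plan is adequate. Robust estimation is conditional, is described as a remedy for non-normality, and is not tied to cohort. At participant level it leaves about 9-15% when cohorts differ in growth. The text permits both the adequate and the inadequate model.

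**Conclusion.** The concern holds in conditional form. The only dependence structure stated in numbers is a constant correlation, which does not suit weeks counted from zero, and the plan does not commit to a model or standard error that protects the arm-by-time test. Depending on choices still open, simulated type I error runs from about nominal to 39%: about 14-25% without and 23-39% with cohort differences on the simplest reading, and about 4-9% with clustering on cohort.

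These sizes assume constant weekly job-start rates, assumed job-loss and re-hire rates, complete data on 240 Veterans, cohorts of 8 in both arms, and no site or covariate terms. The direction does not depend on the exact rates, since inflation appeared across the ranges tried. The hurdle branch is unquantified. Because this is the primary test and the better method is cheap, the text should be settled before analysis.

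**What to change.** In SAP Hypothesis 1 and protocol 5.6 Data Analysis:

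1. Specify an unstructured within-participant visit covariance, or participant random slopes, together with a cohort-by-time random effect.
2. Use small-sample-corrected standard errors clustered on group cohort in every case, not only when non-normality is seen. Say how cohort is handled in the hurdle model.
3. State whether weeks are cumulative or per interval, and which occasions enter the model.
4. Re-run the power simulation with everyone at zero at baseline and cohort variance in growth, and restate the power figure.

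The cost is SAP and protocol wording and one simulation, with no new data or participants. Intervals will be somewhat wider and the stated power may fall. Other structures could also be adequate, provided that cohort differences in growth enter the standard error of the tested term.

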### *Standard Care: VHA Supported Employment (SE) Services*

Participants in both study arms will receive standard SE services during the entire study period. SE services are individualized; vocational specialists meet one-on-one with Veterans and provide job assistance tailored to their needs and preferences. SE services are based on the evidence based Individual Placement and Support (IPS) model that includes the following main tenets: a zero exclusion policy, a brief vocational assessment, rapid job search, job development, including dynamic engagement with employers in the community to identify and secure jobs, job carving (i.e. working with employers to create jobs based on veteran needs), integration with mental health services, benefits counseling, and follow-along support after job acquisition. Further, VACO does periodic fidelity assessments to ensure quality at the 3 SE programs (all have good fidelity to IPS model). VISN learning communities supporting IPS implementation are also available.

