#### *Other measures and covariates*

Sociodemographic and background questionnaire (Appendix 10): Used broadly in previous work studies, a standard background and demographic questionnaire will probe gender, age, ethnicity, education, medical conditions, substance use, military history, residential status, disability entitlements, and legal history. Given its association with future work outcomes found in past studies, work history will be assessed via self-report, CAPRI/VCPRS/JLV chart review, and SE staff report for verification; these variables will include longest past competitive job, weeks worked and wages earned in the 6 and 9 months preceding baseline. Collected via CAPRI/CPRS/JLV chart review, time spent in SE services, operationally defined as the number of days receiving SE services, will be examined as a possible covariate. Session attendance for CBTw and psychoeducation will also be tracked.

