## **5.7 Withdrawal of Subjects**

To further ensure the rights of participants and minimize potential risks, participants will be clearly informed that they may withdraw from the study at any time without any repercussions; participants will continue to receive all VA care and rehabilitation services (including supported employment) as usual, regardless of their study status. Withdrawn participants will not be able to continue in audio recorded groups conducted for the purposes of this study nor complete outstanding assessments. If requested upon withdrawal, the participants' data will be removed from the study to the extent possible. If a participant wishes to withdraw, they will be directed to contact the research assistant at their site to provide a reason for withdrawal.

If during the course of the study the participant formally dis-enrolls in supported employment services, their participation in the study will be terminated. We do not anticipate these circumstances occurring often, as they have not occurred in any of our previous studies of CBTw.

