Aim 2: Health and recovery outcomes. Two-level linear regression models accounting for the nested nature of the data (repeated measures nested within individuals) will be used to examine the effects of CBTw + SE services compared to psychoeducation + SE on the change of each of the continuous outcomes including recovery (RAS), health-related quality of life (PCS & MCS), symptoms (DSM), and suicidality (SSI) over time (baseline and 3-, 6-, 9-months follow-ups). It is expected that there will be adequate power (>80%) to detect the treatment effect on health and recovery outcomes even if the effect size is small (i.e., $f^2 = .03$). *Regarding the outcome of suicidal ideation, it is anticipated that the range of responses will be smaller, given that fewer participants will report these thoughts (21.2% of participants in the CBTw open pilot reported passive ideation at baseline; 9.6% reported such thoughts at follow up). Thus, the study may be less powered to detect a treatment effect. However, despite this issue of range restriction given the relatively lower base rate of suicidal thoughts, WORKWELL will nonetheless examine possible treatment effects, due to the importance of this outcome in Veterans with SMI.*

Preliminary analysis: Baseline characteristics of sample & covariates analyses

Given the RCT design, characteristics of participants are expected to be balanced across the two study arms. Baseline characteristics and baseline clinical outcomes (e.g., symptoms) will be compared between the arms using the appropriate test (i.e., t-test, or Chi-square test). Variables found to significantly differ will be included as covariates in the primary analyses. All primary analyses will also include time receiving SE services and site membership as covariates. The potential interaction effects of site with key predictors will also be included as predictors to account for the site effect. Lastly, attendance (the number of CBTw or psychoeducation sessions attended) and the association with the Aim 1 and Aim 2 outcomes will be examined.

Aim 1 Analyses: Competitive Work Outcomes

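### Primary-model covariates are picked by baseline significance tests and work history is not prespecified; SE days have no cut-off at randomisation and the site interactions no defined trial effect

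*SAP*

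**What the plan says.** **Selection rule.** Under Preliminary analysis the SAP plans balance tests: "Baseline characteristics and baseline clinical outcomes (e.g., symptoms) will be compared between the arms using the appropriate test" (t-test or chi-square). It then says: "Variables found to significantly differ will be included as covariates in the primary analyses". No candidate list or test level is given. Protocol section 5.6 Data Analysis, Preliminary Analyses, has the same rule.

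**Work history.** Protocol section 5.6, Other measures and covariates, gives its link with later work outcomes in past studies as the reason to collect it: "these variables will include longest past competitive job, weeks worked and wages earned in the 6 and 9 months preceding baseline". No analysis section of either document names these variables. The Hypothesis 1 model has only an unspecified covariates term.

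**SE days.** The SAP says: "All primary analyses will also include time receiving SE services and site membership as covariates". The protocol's definition reads: "time spent in SE services, operationally defined as the number of days receiving SE services, will be examined as a possible covariate". That definition has no cut-off at randomisation, and it makes optional what the SAP and the protocol's Preliminary Analyses make mandatory. Section 5.2.2 says: "Participants in both study arms will receive standard SE services during the entire study period". Section 5.7 adds that when someone "formally dis-enrolls in supported employment services, their participation in the study will be terminated".

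**Site.** "The potential interaction effects of site with key predictors will also be included as predictors to account for the site effect". The Hypothesis 1 model repeats these terms. Neither document says which predictors are key, how site is coded, or which contrast is the trial effect.

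**The concern.** Under randomisation, a significant baseline difference is a chance event. Selecting on it leaves the primary model unknown until the arms have been compared, and it ignores whether a variable predicts the outcome. A strong predictor that happens to be balanced stays out; a useless one that happens to differ goes in. The SAP gives the logistic model for steady work the same predictors. There the odds ratio is conditional on whatever was selected, so selection also changes what is estimated.

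SE days raise a different problem. If days after randomisation are counted, the covariate can depend on arm, on finding a job and on staying in the study. Adjusting for it can then move the arm effect.

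Site-by-arm terms in the confirmatory model raise a third. Unless the contrast is defined, the coefficient labelled arm may be the effect at one site.

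**Working it through.** **1. The plan's power figure.** Inputs from the SAP's power section: N = 276, attrition 13%, f² = .03 for arm by time, alpha .05 (two-sided assumed), ICC .077 for cohort and .2 for repeated measures. Cohorts hold up to 8 (protocol 5.2.2). Retained: 276 × .87 = 240. Assuming three follow-up waves there are 720 observations. Design effects are 1 + 7 × .077 = 1.539 (cohort) and 1 + 2 × .2 = 1.4 (repeated measures). Noncentrality is .03 × effective observations.

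| Design effect applied | Effective observations | Noncentrality | Power |
|---|---|---|---|
| Neither | 720 | 21.6 | 99.6% |
| Repeated measures | 514 | 15.4 | 97.5% |
| Cohort | 468 | 14.0 | 96.2% |
| Both | 334 | 10.0 | 88.4% |

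The stated 97.6% is reachable but not determined, because the waves, the time coding and the denominator of f² are not given. It is taken as stated below.

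**2. Selection by chance.** With k independent balance tests at 5% (level assumed), P(at least one enters) = 1 − .95^k. For k = 10 this is .40 and for k = 20 it is .64 (k is assumed, as there is no candidate list). For the five work-history variables it is 1 − .95^5 = .23, and less if they are correlated. A simulation of 20,000 trials used 120 per arm, independent observations, a covariate with R² = .20 and an effect of (1.960 + .842) × √(2/120) = .362 SD. Test-then-adjust had 80.4% power, against 87.5% when always adjusted. With no true effect its type I error was 4.5%. Mean bias was about zero.

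**3. Precision under the SAP's ICCs.** Set the total variance to .077 (cohort) + .2 (person) + .723 (residual) = 1, with 120 per arm in 15 cohorts of 8. A person-level covariate explaining R² of total variance can only reduce the .2. For the 6-month contrast:

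SE = √{2[.077/15 + (.2 − R²)/120 + .723/120]}; power = Φ(2.802 × .1602/SE − 1.960); equivalent N = 276 × (.1602/SE)².

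| R² (assumed) | SE | Power | Equivalent N |
|---|---|---|---|
| 0 | .1602 | 80.0% | 276 |
| .05 | .1575 | 81.3% | 286 |
| .10 | .1549 | 82.6% | 295 |
| .20 (maximum) | .1494 | 85.2% | 317 |

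For arm by linear time, with waves coded −1, 0, 1, SE = √{2 × .723/(120 × 2)} = .0776. The between-person variance does not appear, so a covariate main effect changes nothing.

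**4. SE days.** If arm shifts the covariate by a SD and its slope on the outcome is r, adjustment moves the arm coefficient by −a × r. With a from −.3 to +.3 and r from .1 to .4 (both assumed), the largest shift is .3 × .4 = .12 SD in either direction, and .12/.362 = 33% of the effect in step 2. With days cut at randomisation, a = 0 in expectation and the shift is zero.

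**5. Site interactions.** Power of 97.6% implies z = 1.977 + 1.960 = 3.937. Under reference coding with three equal sites, the arm coefficient uses one third of the sample: 3.937/√3 = 2.273, and Φ(2.273 − 1.960) = .62. From an 80% base, 2.802/√3 = 1.618, and Φ(1.618 − 1.960) = .37. Centred coding largely removes the loss.

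**The case against.** The strongest defence is that nothing here invalidates the primary test. Adjusting for a baseline variable that differs by chance is legitimate, and step 2 shows no average bias and a slightly conservative type I error. A reader might infer that baseline testing itself biases the estimate; the calculation does not support that. The 40 to 64% counts how often a covariate is selected and does not measure harm.

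A reader might also infer that work history is excluded. It is not. The protocol lists it under a heading that mentions covariates, and it can enter through the significance rule or the open covariates term. The accurate statement is that it is not prespecified.

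It is tempting to size the gain as 276/(1 − R²), which gives 291 to 345 for R² of .05 to .20. That assumes independent observations at one time point. The SAP's ICCs reduce it to 286 to 317, and the powered arm-by-time contrast gains nothing. Precision still matters because the named endpoints are time points: 6 months in the protocol, 6 and 9 months in the SAP.

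On SE days, the sponsor may intend a baseline count. The protocol defines the item next to pre-baseline work history, and the SAP uses it under a baseline heading. If days mean enrolment, follow-up days would also be nearly constant among participants who stay, since leaving SE ends participation and the protocol reports no such case in earlier studies of the intervention. This stands as a reason not to claim that bias will occur. It does not settle the definition: the sentence after it concerns session attendance, which is post-randomisation, and days receiving services could mean contacts.

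On site, no text says that a raw reference-coded coefficient will be reported, so 62% is a conditional figure and not the trial's power.

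**Conclusion.** The point holds in a limited form. The primary model is not fixed in advance: its covariates depend on chance imbalance, and the variables the protocol itself regards as predictive are not named.

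- **Precision:** about 1 to 5 power points at 6 months from an 80% base. This assumes that work history explains 5 to 20% of variance, normal outcomes, equal arms, and the SAP's .2 read as the between-person share. The gain is zero for arm by linear time with a random intercept. If the hurdle model is used, these linear-model figures do not apply.
- **Bias:** only SE days counted after randomisation carry this risk, up to about 0.12 SD either way under assumed values. The documents leave open whether such days are counted.
- **Site interactions:** a problem of interpretation and power, and only under reference coding with one coefficient read as the trial result. Site as a main effect is sound.

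The 97.6% is neither confirmed nor shown to be wrong. The wording should be settled before outcomes are compared by arm.

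**What to change.** Make the same changes in the SAP (Preliminary analysis and Aim 1 Analyses) and in protocol section 5.6 Data Analysis (Preliminary Analyses and Hypothesis 1), so that the documents agree:

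1. Delete the significance rule. Baseline tables can stay descriptive.
2. Name the covariates: site, SE days accrued before randomisation, and specified work-history variables, for example competitive weeks worked in the 9 months before baseline and longest past competitive job.
3. Reconcile the optional status of SE time under Other measures and covariates with its mandatory status in the analysis sections, and add the cut-off at randomisation to the definition.
4. Move site interactions to the analysis already planned under Account for Heterogeneity in the Sample, or keep them and define the trial effect as the average over sites.

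Do not add the baseline score as a covariate to the Hypothesis 2a models. The SAP already treats baseline as one of the outcome time points there, and Hypothesis 2b already controls for baseline levels.

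The cost is wording in two documents and a few degrees of freedom. The variables are already collected.
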